2.7.2 Statistical hypothesis, model, and method of analysis

Overall Survival

The survival distribution of OS distribution will be estimated using the Kaplan-Meier method. The Kaplan-Meier curve will be graphically presented, and the median, 25th and 75th percentiles will be shown along with the corresponding 95% confidence intervals [\[Brookmeyer and Crowley 1982\]](#) along with the proportion of patients alive at 6, 12 and 24 months and the associated 95% confidence intervals will be presented.

ORR (same for CBR)

ORR and CBR will be summarized using descriptive statistics (N, %) along with two-sided exact binomial 95% CIs [\[Clopper and Pearson 1934\]](#).

DOR (same for time to response)

DOR will be summarized for all patients in the FAS with confirmed BOR of CR or PR. DOR will be estimated using the Kaplan-Meier method. The Kaplan-Meier curve will be graphically presented and median, 25th and 75th percentiles, and the corresponding 95% confidence intervals will be provided.

2.7.3 Handling of missing values/censoring/discontinuations

Overall Survival

If a patient is not known to have died at the time of analysis cut-off, then OS will be censored at the date of last known date patient was alive, i.e., last contact date (see [Section 2.1.1](#)).

ORR (same for CBR)

Patients with unknown or missing best overall response (BOR) will be counted as failures. If there is no baseline tumor assessment, all post-baseline overall lesion responses are expected to be ‘Unknown’. If no valid post-baseline tumor assessments are available, the best overall response must be “Unknown” unless progression is reported. For the computation of ORR, these patients will be included in the FAS and will be counted as ‘failures’.

2.8 Safety analyses

All safety analyses will be based on the safety set.

The overall observation period will be divided into three mutually exclusive segments:

1. pre-treatment period: from day of patient’s informed consent to the day before first dose of study medication;
2. on-treatment including safety follow-up period: from day of first dose of study medication to 30 days after last dose of study medication;
3. post-treatment period: starting at day 31 after last dose of study medication.

2.8.1 Adverse events (AEs)

AE summaries will include all AEs occurring during on treatment period. All AEs collected in the AE eCRF page will be listed along with the information collected on those AEs e.g. AE relationship to study drug, AE outcome etc. AEs with start date outside of on-treatment period will be flagged in the listings.

AEs will be summarized by number and percentage of patients having at least one AE, having at least one AE in each primary system organ class (SOC) and for each preferred term (PT) using MedDRA coding. A patient with multiple occurrences of an AE will be counted only once in the respective AE category. A patient with multiple CTCAE grades for the same preferred term will be summarized under the maximum CTCAE grade recorded for the event. AE with missing CTCAE grade will be included in the ‘All grades’ column of the summary tables.

In AE summaries, the primary system organ class will be presented alphabetically and the preferred terms will be sorted within primary SOC in descending frequency. The sort order for the preferred term will be based on their frequency.

The following adverse event summaries will be produced; overview of adverse events and deaths, AEs by SOC and PT, summarized by relationship, seriousness (SAEs and non-SAEs), leading to treatment discontinuation, leading to dose interruption/adjustment, requiring additional therapy and leading to fatal outcome.

The summary of overview of all adverse events will be presented for line of therapy subgroups as specified in [Section 2.2.1](#).

2.8.1.1 Adverse events of special interest / grouping of AEs

Adverse events of special interest (AESI) are defined as events (serious or non-serious) which are ones of scientific and medical concern specific to the sponsor's product or program, for which ongoing monitoring and rapid communication by the investigator to the sponsor may be appropriate. Such events may require further investigation in order to characterize and understand them.

Adverse events of special interest are defined on the basis of an ongoing review of the safety data. AESIs are discussed in detail in the Investigator Brochure. The latest Case Retrieval Strategy (CRS) available at the time of the Primary/Final analysis will be used.

AESIs for this trial include hepatic toxicity, hypertension, thyroid-related disorders (hypothyroidism) and cardiac dysfunction.

Data analysis of AESIs

An adverse event of special interest is a grouping of adverse events that are of scientific and medical concern specific to compound pazopanib. These groupings are defined using MedDRA terms, SMQs (standardized MedDRA queries), HGLTs (high level group terms), HLT (high level terms) and PTs (preferred terms). Customized SMQs (Novartis MedDRA queries, NMQ) may also be used. A NMQ is a customized group of search terms which defines a medical concept for which there is no official SMQ available or the available SMQ does not completely fit the need. It may include a combination of single terms and/or an existing SMQ, narrow or broad. For each specified AESI, number and percentage of patients with at least one event of the AESI occurring during on treatment period will be summarized.

Summaries of these AESIs will be provided, (specifying grade, SAE, relationship, leading to treatment discontinuation, leading to dose adjustment/interruption etc.).

2.8.2 Deaths

Separate summaries for on-treatment and all deaths will be produced by system organ class and preferred term.

All deaths will be listed, post treatment deaths will be flagged. A separate listing of deaths prior to starting treatment will be provided for all screened patients.

2.8.3 Laboratory data

On analyzing laboratory, data from all sources (central and local laboratories) will be combined. The summaries will include all assessments available for the lab parameter collected no later than 30 days after the last study treatment administration date (see [Section 2.1.1](#)).

The following summaries will be produced for hematology and biochemistry laboratory data (by laboratory parameter and treatment):

- Worst post-baseline CTC grade (regardless of the baseline status) will be presented for safety population . Each patient will be counted only for the worst grade observed post-baseline.

The following listing will be produced for the laboratory data:

- Listing of all CTC grade 3 or 4 laboratory toxicities.

Liver function parameters

Liver function parameters of interest are total bilirubin (TBL), ALT, AST and alkaline phosphatase (ALP). The number (%) of patients with worst post-baseline values as per Novartis Liver Toxicity guidelines will be summarized:

The following summaries will be produced:

- ALT or AST > 3xULN
- ALT or AST > 5xULN
- ALT or AST > 8xULN
- ALT or AST > 10xULN
- ALT or AST > 20xULN
- TBL > 2xULN
- TBL > 3xULN
- ALT or AST > 3xULN & TBL > 2xULN
- ALT or AST > 3xULN & TBL > 2xULN & ALP < 2xULN (potential Hy's law)

Potential Hy's Law events are defined as those patients with concurrent occurrence of AST or ALT > 3xULN and TBL > 2xULN and ALP < 2xULN in the same assessment sample during the on-treatment period. Further medical review has to be conducted to assess potential confounding factor such as, liver metastases, liver function at baseline etc.

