10.5.3.3 Laboratory abnormalities

Grading of laboratory values will be assigned programmatically as per NCI Common Terminology Criteria for Adverse Events (NCI-CTCAE) version 4.03. The calculation of NCI-CTCAE grades will be based on the observed laboratory values only, clinical assessments will not be taken into account.

NCI-CTCAE Grade 0 will be assigned for all non-missing values not graded as 1 or higher.

For laboratory tests where grades are not defined by NCI-CTCAE v4.03, results will be categorized as low/normal/high based on laboratory normal ranges.

For laboratory tests where grades are defined by NCI-CTCAE v4.03:

- Worst post-baseline NCI-CTCAE grade (regardless of the baseline status). Each patient will be counted only once for the worst grade observed post-baseline.
- Shift tables using NCI-CTCAE grades to compare baseline to the worst on-treatment value

For laboratory tests where grades are not defined by NCI-CTCAE v4.03:

- Shift tables using the low/normal/high/ (low and high) classification to compare baseline to the worst on-treatment value.
- Laboratory abnormalities will be summarized for safety set as well as by line of therapy subgroup (2nd/3rd), age and MSKCC and IDMC risk groups, as appropriate.

Listing of all laboratory data with values flagged to show the corresponding NCI-CTCAE v4.03 grade if applicable and the classifications relative to the laboratory normal ranges will be generated.

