5.3 Laboratory parameters derivations

Grade categorization of lab values will be assigned programmatically as per NCI Common Terminology Criteria for Adverse Events (CTCAE) version 4.03 (specify version used in the RAP). The calculation of CTCAE grades will be based on the observed laboratory values only, clinical assessments will not be taken into account. The criteria to assign CTCAE grades are given in Novartis internal criteria for CTCAE grading of laboratory parameters. The latest available version of the document based on the underlying CTCAE version 4.03 at the time of analysis will be used. For laboratory tests where grades are not defined by CTCAE v4.03, results will be graded by the low/normal/high classifications based on laboratory normal ranges.

A severity grade of 0 will be assigned for all non-missing lab values not graded as 1 or higher. Grade 5 will not be used. For laboratory tests that are graded for both low and high values, summaries will be done separately and labelled by direction, e.g., sodium will be summarized as hyponatremia and hypernatremia.

Imputation Rules

CTC grading for blood differentials is based on absolute values. However, this data may not be reported as absolute counts but rather as percentage of WBC.

If laboratory values are provided as '<X' (i.e. below limit of detection) or '>X', prior to conversion of laboratory values to SI unit, these numeric values are set to X.

The following rules will be applied to derive the WBC differential counts when only percentages are available for a xxx differential

$$\text{xxx count} = (\text{WBC count}) * (\text{xxx \%value} / 100)$$

Further derivation of laboratory parameters might be required for CTCAE grading. For instance, corrected calcium can be derived using the reported total calcium value and albumin at the same assessment using the following formula:

$$\text{Corrected Calcium (mg/dL)} = \text{Calcium (mg/dL)} - 0.8 [\text{Albumin (g/dL)} - 4]$$

In order to apply the above formula, albumin values in g/L will be converted to g/dL by multiplying by 0.1), calcium values in mmol/L will be converted to mg/dL by dividing by 0.2495. For calculation of laboratory CTC grades 0 and 1, the normal range for derived corrected calcium is set to the same limits (in mg/dL) as for calcium.

CTC grades for the derived absolute WBC differential counts (neutrophils, lymphocytes) and corrected calcium will be assigned as described above for grading

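### SAP 2.8.3 omits the baseline-to-worst laboratory shift tables planned in protocol 10.5.3.3, and SAP section 4 does not declare the change

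*SAP*

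**What the plan says.** Protocol 10.5.3.3 sets its laboratory outputs without restricting them to particular panels. For graded tests it pairs a worst-grade table with "Shift tables using NCI-CTCAE grades to compare baseline to the worst on-treatment value". For ungraded tests it names one table type only: "Shift tables using the low/normal/high/ (low and high) classification to compare baseline to the worst on-treatment value".

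SAP 2.8.3 opens with "The following summaries will be produced for hematology and biochemistry laboratory data (by laboratory parameter and treatment" and lists a single general table under it: "Worst post-baseline CTC grade (regardless of the baseline status) will be presented for safety population". It adds counts of patients crossing liver-test thresholds, and a "Listing of all CTC grade 3 or 4 laboratory toxicities". SAP 5.3 still classifies the other tests: "For laboratory tests where grades are not defined by CTCAE v4.03, results will be graded by the low/normal/high classifications".

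SAP section 4 declares three departures from the protocol: therapy summaries moved to the FAS, the Per-Protocol Set dropped, and AESI names updated. SAP section 1 presents the document as covering every analysis planned for the study report, so a table it does not mention is not planned.

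**The concern.** Laboratory toxicity is part of a stated secondary endpoint (protocol Table 3-1, SAP Table 1-1). With no control arm, the only way to separate what a patient brought into the study from what appeared on pazopanib is to compare with that patient's own baseline. The protocol does this with the shift tables. Without them, a reader of the study report sees how many patients were ever at each grade after baseline, but not how many moved there.

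Thyroid disorders are an adverse event of special interest (protocol 8.1.3). Free T3, free T4 and TSH are therefore among the tests where a movement table would be most useful.

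**Working it through.** The plan gives no figure to reproduce. The check sets the two documents side by side and then asks whether the loss can matter.

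**1. Planned against kept**

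| Laboratory summary in protocol 10.5.3.3 | In the SAP |
|---|---|
| Worst post-baseline grade | Kept, for hematology and *biochemistry* (2.8.3) |
| Grade shift, graded tests | Not planned |
| Normal-range shift, ungraded tests | Not planned |
| Summaries by subgroup, at discretion | Not planned |

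Declared changes in SAP section 4 that concern laboratory data: 0 of 3. The lean-SAP reason given there is attached to the Per-Protocol Set only.

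**2. Consequence for ungraded tests.** The one general table reports CTCAE grades, so it cannot show a test that has none. SAP 5.3 derives the normal-range class, but no table uses it. Ungraded tests therefore have no summary, even within hematology and chemistry.

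**3. Thyroid and coagulation.** Protocol Table 7-5 lists these apart from the chemistry rows, and the SAP does not define *biochemistry*. On either reading they have no shift table. If the word means the Table 7-5 chemistry rows, they have no summary table at all.

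**4. Is an older protocol version the reason?** The SAP cites protocol v01 and uses the design of about 100 patients, 40 of them second-line, that Amendment 1 introduced. For section 10.5.3.3, that amendment's change list mentions only added subgroup tabulations. Amendment 2's list concerns pregnancy follow-up and an imaging window. Nothing suggests that the shift tables postdate the SAP.

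**5. Can baselines be abnormal?** From protocol 5.2, criterion 8:
- Platelets may be as low as 100 x 10^9/L = 100,000/mm3. In Table 6-2, grade 1 runs from the lower limit of normal down to 75,000/mm3. A patient entering between 100,000/mm3 and that limit is already grade 1. Nobody eligible enters at grade 2 or above, so for platelets the ambiguity is confined to grade 1.
- Hemoglobin may be as low as 9 g/dL. The MSKCC cut-offs (13 g/dL for men, 11.5 g/dL for women) and the IMDC factor (below the normal limit) show that low values are expected at entry.
- Creatinine above 1.5 mg/dL is allowed with adequate clearance or eGFR. Table 6-2 lets grade 2 creatinine recover to grade 1 or to baseline, which anticipates raised starting values.
- Potassium, sodium, calcium and magnesium must be normal at screening, so the problem largely disappears for these.

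**6. Illustration, on assumed rates.** Let b be the share entering at grade 1 or higher and still there after baseline, and let 20% of the others reach grade 1 or higher. The worst-grade table then shows b + (1 - b) x 0.20:
- b = 0: 20%
- b = 0.10: 0.10 + 0.18 = 28%
- b = 0.20: 0.20 + 0.16 = 36%
- b = 0.30: 0.30 + 0.14 = 44%

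The true rate of new abnormality among patients normal at entry is 20% in every row. The documents give no baseline-grade rates, so this shows the mechanism and not the trial's expected result.

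**The case against.** The best defence is that much of laboratory safety remains. The worst-grade table and liver thresholds are kept, and abnormalities that need treatment or a dose change are adverse events and appear in the AE and AESI tables. Ignoring baseline in the worst-grade table is also the protocol's own specification and not a SAP change. All of this stands and keeps the point small. It does not close the gap. Protocol 8.1.2.1 keeps abnormalities that are not adverse events out of AE reporting, and what the SAP removed is the companion table that made the worst-grade table interpretable. SAP 2.1.1 mentions change-from-baseline summaries as a general example, but no laboratory one is specified.

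A reader might infer more than the documents support:
- **That every thyroid, coagulation and urine table is lost.** This depends on an undefined word. UPC is scheduled only at screening and end of treatment, and 24-hour urine only when indicated, so a count of missing panels would be inflated. The protocol's proteinuria limits are entry and dosing rules, not planned analysis cut-points.
- **That dropping the subgroup summaries breaks the protocol.** It says "Laboratory abnormalities will be summarized for safety set as well as by line of therapy subgroup" and by other factors, but qualifies this as discretionary. Protocol section 10 promises only selected safety analyses by subgroup. Leaving them out is defensible, though it should be stated.
- **That the listing is cut to grades 3 and 4.** The protocol plans a "Listing of all laboratory data with values flagged to show the corresponding NCI-CTCAE v4.03 grade". SAP 2.1.1 still lists all safety data, and the grade 3-4 listing can be read as an addition.

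**Conclusion.** The point holds for the shift tables. Both types are planned in the protocol without qualification, both are absent from the SAP, and the omission is undeclared. Ungraded tests are left without a summary, and thyroid and coagulation without a shift table on any reading. The kept table can mix pre-existing with on-treatment abnormality for tests where entry permits abnormal values.

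Severity is minor. No data are lost, and how many patients would be misread cannot be derived from the documents. The conclusion rests on reading the SAP's silence as omission, which its own statement of scope supports. The stronger statement that thyroid and coagulation have no table at all rests on the Table 7-5 reading of *biochemistry*.

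**What to change.** In SAP 2.8.3, for the Safety Set:
- Add CTCAE grade shift tables, baseline to worst on-treatment value, for hematology and chemistry.
- Add shift tables by low, normal, high, and both low and high for ungraded tests, including thyroid and coagulation (by grade for any of these tests that has one).
- State which panels *biochemistry* covers.

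In SAP section 4, declare any protocol-planned laboratory output that is deliberately not produced, including the discretionary subgroup summaries. Special urine-protein tables, subgroup tables and a revised listing are not needed to settle this point.

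Cost: no new assessments. Assuming one table per panel and type, the count is 2 grade shifts + 1 to 2 for ungraded hematology and chemistry + 1 to 2 for thyroid + 1 to 2 for coagulation = 5 to 8 tables. Each declaration costs one sentence. The downside is some extra output in a SAP meant to be lean.

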2.8.4 Other safety data

NA

2.8.4.1 ECG and cardiac imaging data

Data handling

In case the study requires ECG replicates at any assessment, the average of the ECG parameters at that assessment should be used in the analyses.

Data analysis

Local 12-lead ECGs including HR, PR, QRS, and QT intervals will be obtained for each patient at baseline, during the study treatment period and at the end of treatment. ECG data will be read and interpreted locally.

The number and percentage of patients with notable ECG values will be presented.

- QT or QTcF
 - New value of > 450 and ≤ 480 ms
 - New value of > 480 and ≤ 500 ms
 - New value of > 500 ms
 - Increase from Baseline of > 30 ms to ≤ 60 ms
 - Increase from Baseline of > 60 ms
- HR
 - Increase from baseline $> 25\%$ and to a value > 100 bpm
 - Decrease from baseline $> 25\%$ and to a value < 50 bpm
- PR
 - Increase from baseline $> 25\%$ and to a value > 200 ms
 - New value of > 200 ms
- QRS
 - Increase from baseline $> 25\%$ and to a value > 120 ms
 - New values of QRS > 120 ms

A listing of notable values of ECG parameters will be produced and the assessments collected during the post-treatment period will be flagged.

2.8.4.2 Vital signs

Vital sign assessments are performed in order to characterize basic body function. The following parameters were collected: height (cm), weight (kg), body temperature ($^{\circ}\text{C}$), heart rate (beats per minute), systolic and diastolic blood pressure (mmHg).

Data handling

Vital signs collected on treatment will be summarized. Values measured outside of on treatment period will be flagged in the listings.

Data analysis

For analysis of vital signs the clinically notable vital sign criteria are provided in [Table 2-6](#) below.

Table 2-6 Clinically notable changes in vital signs

Vital sign (unit)	Clinically notable criteria	
	above normal value	below normal value
Weight (kg)	increase $> 10\%$ from Baseline	decrease $> 10\%$ from Baseline
Systolic blood pressure (mmHg)	≥ 150 with increase from baseline of ≥ 20	≤ 90 with decrease from baseline of ≥ 20

Vital sign (unit)	Clinically notable criteria	
	above normal value	below normal value
Diastolic blood pressure (mmHg)	>=100 with increase from baseline of >=15	<=50 with decrease from baseline of >=15
Pulse rate (bpm)	>=100 with increase from baseline of >25%	<=50 with decrease from baseline of > 25%
Body temperature	>= 39.1	-

The number and percentage of patients with notable vital sign values (high/low) will be presented.

A listing of notable values of vital sign parameters will be produced and the assessments collected outside of on-treatment period will be flagged.

2.8.4.3 Additional Analyses: Echocardiogram/MUGA

Data handling

In case the study requires ECHO/MUGA replicates at any assessment, the average of the LVEF at that assessment should be used in the analyses.

Data analysis

Local echocardiogram or MUGA will be obtained for each patient will be obtained at baseline, during the study treatment period and at the end of treatment. The number and percentage of patients with notable post-baseline values of left ventricular ejection fraction (LVEF) based on NCI-CTCAE v4.03 will be summarized on the Safety Set:

- Grade 2: LVEF between ≥ 40 and ≤ 50 % and/or decrease from baseline between ≥ 10 and < 20 %
- Grade 3: LVEF between < 40 and ≤ 20 % and/or decrease from baseline between > 20 %
- Grade 4: LVEF < 20 %

In addition, the following notable post-baseline values will also be described on the Safety Set:

- Number of patients with new LVEF (%) $< 50\%$
- Number of patients with new LVEF (%) $< 50\%$ and decrease $> 10\%$
- Number of patients with new LVEF (%) $< 50\%$ and decrease $> 20\%$

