10.5.3.4 Other safety data

ECG

- Local 12-lead ECGs including HR, PR, QRS, QT, and QTcF intervals will be obtained for each subject at baseline, during the study treatment period and at the end of treatment. ECG data will be read and interpreted locally.
- The number and percentage of patients with notable ECG interval values and change from baseline ECG parameters by time point will be summarized in the Safety set.
- All collected data will be presented in data listings; notable values and abnormality finding will be flagged in the listing.

Echocardiogram/MUGA

- Local echocardiogram or MUGA will be obtained for each subject at baseline, during the study treatment period and at the end of treatment.
- Ejection fraction values will be classified based on NCI-CTCAE v4.03 and a shift table will be prepared for the Safety set to summarize the distribution of individual worst on-treatment values vs. the corresponding baseline values.
- All collected data will be presented in data listings and notable values will be flagged.

Vital signs

- Data on vital signs will be tabulated and listed, notable values will be flagged.

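### SAP 2.8.4.3 prints LVEF Grade 3 with an inverted bound and does not define the unit of decrease; separately, the protocol's LVEF and laboratory shift tables are missing from the SAP without being declared

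*SAP*

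**What the plan says.** **LVEF grades.** SAP 2.8.4.3 plans counts of notable post-baseline LVEF by NCI-CTCAE v4.03 grade and prints its own bands. Grade 2 is "Grade 2: LVEF between ≥ 40 and ≤ 50 % and/or decrease from baseline between ≥ 10 and < 20" %, Grade 3 is "Grade 3: LVEF between < 40 and ≤ 20 % and/or decrease from baseline between > 20" %, and Grade 4 is below 20%. Three further counts, each beginning "Number of patients with new LVEF", cover new values below 50%: alone, with a decrease above 10%, and with a decrease above 20%.

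**Shift tables in the protocol.** For LVEF, section 10.5.3.4 says that "a shift table will be prepared for the Safety set to summarize the distribution of individual worst on-treatment values" against baseline. For laboratory data, section 10.5.3.3 asks for "Shift tables using NCI-CTCAE grades to compare baseline to the worst on-treatment value" and, for tests without CTCAE grades, "Shift tables using the low/normal/high/ (low and high) classification to compare baseline to the worst on-treatment value".

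**What the SAP keeps.** For haematology and biochemistry, SAP 2.8.3 gives "Worst post-baseline CTC grade (regardless of the baseline status) will be presented for safety population", a "Listing of all CTC grade 3 or 4 laboratory toxicities", and counts above liver thresholds. SAP 2.8.4.3 gives only the LVEF counts above. No shift table appears in SAP 2.8. SAP Section 4 declares three changes: the analysis set for therapies, the dropped per-protocol analysis, and updated AESI names.

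**The concern.** The LVEF rule cannot be programmed as printed without a private decision on what was meant, and two programmers could grade the same patient differently. Coded literally, the table could understate some falls to 21–39%. Cardiac dysfunction is an adverse event of special interest in this trial.

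The shift tables matter because the trial has one arm, so each patient's own baseline is the only internal reference. A worst-grade table that ignores baseline cannot by itself separate an abnormality present at entry from one that arose on treatment. The same holds for LVEF. No minimum LVEF is set for entry (a history of cardiac failure is excluded), so an unchanged 45% counts as Grade 2 by value.

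**Working it through.** **1. Value bands as printed (SAP 2.8.4.3).** The condition <40 and ≤20 reduces to ≤20. Over whole values 5–50:

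| LVEF (%) | As printed | With Grade 3 read as ≥20 and <40 |
|---|---|---|
| 40–50 | Grade 2 | Grade 2 |
| 21–39 (19 values) | none | Grade 3 |
| 20 | Grade 3 | Grade 3 |
| 5–19 (15 values) | Grades 3 and 4 | Grade 4 |

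**2. How far the fall criterion rescues 21–39%.** The fall is baseline minus post-baseline in points, or 100 × (baseline − post)/baseline as relative change. Taking the highest grade met, for baselines 40–75 and post-baseline 21–39:
- In points, only baselines 40–59 have pairs below Grade 3. From baseline 60 every such fall is at least 60 − 39 = 21.
- As relative change, only baselines 40–48 do. At 49 the smallest fall is 10/49 = 20.4%.
- Examples in points: 55 to 35 (fall 20) ungraded; 50 to 38 (fall 12) Grade 2; 45 to 36 (fall 9) ungraded.
- For baselines 50–75 in points, of 26 × 19 = 494 pairs, 439 are already Grade 3, 45 are Grade 2 and 10 are ungraded. All 10 are falls of exactly 20.

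**3. A fall of exactly 20 points, whole baselines 50–75 (26 cases).**

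| Rule | Grade 3 | Grade 2 | Ungraded |
|---|---|---|---|
| As printed | 0 | 11 | 15 |
| ≤20 replaced by ≥20 only | 10 | 11 | 5 |
| Grade 3 as ≥20 and <40, or fall ≥20 | 26 | 0 | 0 |

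Correcting the sign alone leaves 16 of 26 below Grade 3.

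**4. The unit, with all bounds corrected.**
- 60 to 47: 13 points, Grade 2; 13/60 = 21.7%, Grade 3.
- 65 to 58: 7 points, no grade; 7/65 = 10.8%, Grade 2.
- Baselines 50–75, post-baseline from 40 to one below baseline: the grade differs in 190 of 585 pairs (140 Grade 2 against 3, 50 none against Grade 2).
- The extra counts share the ambiguity. For 55 to 48 the fall is 7 points, so it is not counted under a decrease above 10%; as 7/55 = 12.7% it is counted.

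These grid counts show the range of values affected, not expected patient frequencies.

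**5. Laboratory tests where baseline matters.** Protocol Table 7-5 lists 5 liver tests and 15 other chemistry tests, 20 in all. Protocol 5.2 sets entry limits for 8: ALT, AST, total bilirubin, creatinine, potassium, sodium, calcium and magnesium. That leaves 20 − 8 = 12 without one: ALP, direct bilirubin, albumin, phosphate, cholesterol, urea, amylase, lipase, glucose, LDH, uric acid and creatine kinase.
- Lipase at 3 × ULN at entry and unchanged is Grade 3 on the bands in protocol Table 6-2 (>2.0–5.0 × ULN). It would be counted as worst post-baseline Grade 3 if the sponsor's internal grading criteria, which were not supplied, use the same bands.
- Haemoglobin down to 9 g/dL is admitted, and SAP 5.1.3 counts haemoglobin below the lower limit of normal as a risk factor, so low entry values are foreseen. Creatinine above 1.5 mg/dL is admitted if clearance or eGFR is adequate.
- For other tests the loss is small. Potassium, sodium, calcium and magnesium must be normal at screening. With neutrophils ≥1.5 and platelets ≥100 × 10⁹/L at screening, Grade 2 or worse on the Table 6-2 bands is new since screening. The SAP's liver cut-offs (ALT or AST >3 × ULN, bilirubin >2 × ULN) lie above the entry limits.

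SAP 5.3 still classifies ungraded tests as low, normal or high, but no planned table uses that classification.

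**The case against.** The inverted bound rests on one character in machine-read text, and this SAP shows symbol and table damage elsewhere. Grades 2 and 4 leave only 20–40% for Grade 3, so misgrading needs someone to code a visibly contradictory line. Even then 439 of 494 pairs reach Grade 3 through the fall criterion. All of that stands, and it limits the weight of the sign error. It does not reach the exact-20 gap or the unit, which remain with the sign corrected.

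The citation of CTCAE v4.03 might settle the unit for the grades. That standard is not among the documents, the SAP prints its own bands beneath the citation, and the extra counts cite no standard. Taking the worst grade by either criterion is the natural reading of and/or, so the missing rule for conflicting grades is a minor point. The exact-20 gap could also be closed by widening Grade 2 to ≤20; the SAP's strict <20 for Grade 2 favours putting 20 in Grade 3.

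On laboratory data, exclusion 6 requires liver tests below Grade 1 as part of recovery from checkpoint-inhibitor toxicity, and exclusion 21 removes some other abnormal patients. It is not shown which of the 12 tests carry CTCAE grades. SAP 2.1.1 lists all safety data and allows change-from-baseline summaries where appropriate, new LVEF below 50% is counted separately, and treatment-emergent adverse event tables are kept. Shifts could therefore be reconstructed by hand, but the tables the protocol requires are still neither planned nor declared dropped. The SAP's streamlining reason in Section 4 is given only for the per-protocol set.

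**Conclusion.** The concern holds. The Grade 3 value band is wrong as printed, subject to checking the sign in the original PDF. The exact-20 gap and the undefined unit hold whichever way the sign reads. The omission of the shift tables holds on the text alone. The amendment after the protocol version the SAP cites lists changes only to protocol Section 8.4 and Table 7-3. The redacted block after SAP 2.9 lies outside the 2.8 safety sections and Section 4.

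The effect is confined to descriptive safety tables. PFS and the MedDRA-based AESI tables do not change. How many patients would be affected cannot be estimated from the documents. The corrected bounds are inferred from the SAP's own neighbouring grades, not from CTCAE itself. This should be corrected, but it does not threaten the trial's main result.

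**What to change.** In SAP 2.8.4.3:
- State Grade 3 as LVEF ≥20% and <40%, or a fall of ≥20, after checking against CTCAE v4.03.
- Define the unit of decrease once, for the grades and for the two extra counts that use it.
- Say that a patient takes the worst grade met by either criterion. For example, 70 to 45 in points is Grade 2 by value and Grade 3 by its fall of 25.

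For the shift tables, either add the protocol's baseline-to-worst tables for LVEF, graded laboratory tests and low/normal/high tests, or declare and justify their removal in SAP Section 4. Also confirm whether biochemistry in SAP 2.8.3 includes the thyroid panel; this is a query only.

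The cost is a few words in 2.8.4.3 and either standard tables from data already collected or one paragraph in Section 4.
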